# Handling of Missing Data

#### 8.3 PATIENT DISPOSITION

Total number of patients screened, enrolled and failed screening will be summarized on all screened patients, together with reasons for the screen failure; country of enrolled patients will also be summarized. All patients who have signed the informed consent form are considered

Review Status: Draft Version: 2.0 Version Date: 22-JUL-2024

screened; enrolled refers to the eCRF field called "Was Subject enrolled in the study?". Number of patients included in each analysis set and reasons for study discontinuation will also be summarized. Summaries will be done for all enrolled patients, DDS for Phase 1, and for all enrolled patients and Safety Analysis Set for Phase 2a.

Listings of all screened patients, reasons for screen failure, study populations, and inclusion/exclusion criteria not met will be created. Study discontinuation data will also be listed.

#### 8.4 PROTOCOL DEVIATIONS

Protocol Deviations will be summarized by counts and percentages. Major important, major and minor deviations will be summarized separately. Rules for identifying and treating protocol deviations are described in the Protocol Deviations Management Plan. Summaries will be done for all enrolled patients. A listing of all protocol deviations, along with their grade as major important, major or minor, will be provided for all screened patients.

#### 8.5 PATIENT CHARACTERISTICS

All summaries in this section will be done for both Safety Analysis Set and FAS for Phase 1 and Phase 2a.

#### 8.5.1 BASELINE AND DEMOGRAPHIC CHARACTERISTICS

Following characteristics at Baseline will be summarized for the Safety Analysis Set and the FAS:

- Age (years)
- Sex
- Female with childbearing potential (and a reason, if not)
- Race and Ethnicity
- Height
- Weight
- Pulmonary Function test

Smoking history (smoking status, smoking duration in years, number of cigarettes per day and number of years since quitting) and alcohol consumption will be summarized and listed with the demographic characteristics as well.

Listings of the baseline demography data will be prepared for the Safety Analysis Set.

#### 8.5.2 MEDICAL HISTORY AND CURRENT MEDICAL CONDITIONS

Prior Cancer History (Cancer Type, Cancer Stage, Histopathological Type, Extent at Screening, Location of Metastases, Gene Alteration / Protein Overexpression) together with the screening Eastern Cooperative Oncology Group (ECOG) performance status value will be summarized.

Listings of Cancer History data will be created.

Prior and Concurrent medical conditions other than cancer will also be summarized. All conditions will be coded using the Medical Dictionary for Regulatory Activities (MedDRA) version 22.1 or higher. Summaries will be split by System Organ Class (SOC) and Preferred Term (PT). A condition will be considered prior if its end date is prior to the first date of the study

Review Status: Draft Version: 2.0 Version Date: 22-JUL-2024

drug administration. A condition will be considered concurrent if its end date is equal to or greater than the first date of the study drug administration.

Separate listings for Prior and Concurrent conditions will be created.

#### 8.5.3 PRIOR AND CONCOMITANT MEDICATIONS AND PROCEDURES

Prior Cancer Related Surgeries (number of surgeries and residual disease), Cancer Related Radiotherapy (number of radiotherapies and total dose) and Prior Cancer Therapy (number of regimens, regimen type, number of cycles, best response, reason for treatment discontinuation and coded therapy term) for cancer will be summarized. Numbers of prior surgeries and prior lines of treatment are calculated as the number of unique lines recorded on the respective eCRF page. Prior Cancer Therapies will be coded using World Health Organization (WHO) Drug Dictionary from March 2019.

Prior and Concomitant Medications will also be coded according to WHO Drug Dictionary from March 2019. They will be summarized by counts and percentages splitting by ATC2 and ATC4. Medications will be considered prior if the end date is prior to the first date of the study drug administration. A medication will be considered concomitant if its end date is equal to or greater than the first date of the study drug administration.

Separate listings will be created for Prior Cancer Related Surgeries, Radiotherapy Treatments and Therapies, and also for prior and concomitant medications. In addition, listings of Surgeries and other Procedures and Post-Study Anti-Cancer Treatment will be created.

#### 8.6 PRIMARY AND EFFICACY ENDPOINTS AND ANALYSIS

8.6.1 ANALYSIS OF PRIMARY ENDPOINT

[figure not shown]
All the efficacy tables will be run for Full Analysis Set for Phase 1 and for Phase 2a. Where specified additionally, sensitivity analyses on DDS will be run.

Review Status: Draft Version: 2.0 Version Date: 22-JUL-2024

Review Status: Draft Version: 2.0

Version Date: 22-JUL-2024

#### 8.6.2 ANALYSIS OF SECONDARY ENDPOINTS

#### Phase 1 (Dose Escalation)

Non-compartmental analysis will be conducted using concentration time data of AFM24. In addition, a population PK analysis may be conducted. Separate PK analysis plan(s) will be created as applicable, and results will be presented in separate PK report(s). As a part of the analysis described in this SAP, by time point summaries of PK concentration data will be created, grouped by dose level. Plots for individual PK concentrations will be generated as well. PK concentrations will be listed.

Anti-drug Antibodies (ADA) results (both screening and confirmatory results as well as titer) will be summarized by visit and change from baseline to worst-post-baseline. Listing of ADA data

Review Status: Draft Version: 2.0 Version Date: 22-JUL-2024

will be created. The Immunogenicity data will be summarized for the Safety Analysis Set in Phase 1.

The ORR (CR or PR), Disease Control Rate (DCR) [CR or PR or stable disease (SD)] and Clinical Benefit Rate (CBR) [CR or PR or SD ≥24 weeks], assessed by the investigators using RECIST 1.1 will be summarized. Best overall response will be used to define the ORR, DCR and CBR. Best response is defined as the best observed response (CR>PR>SD>PD) throughout the study. See SAP Table 1 for rules of response confirmation. Summaries will include the count and percentages of different best overall responses, ORR, DCR and CBR for each dose level. The percentages will be based on the total number of patients in the Full Analysis Set for a given dose level.

In addition, waterfall plots for percentage change from baseline for sum of longest diameter and swimmer plots showing timing and results of RECIST 1.1 response assessments will be prepared. Waterfall plots will only include tumor assessments that were done at least 42 days after C1D1.

The ORR (CR or PR), DCR (CR or PR or SD) and CBR (CR or PR or SD ≥24 weeks) assessed by the investigators using RECIST 1.1 will be summarized. The best overall response will be used to define the ORR, DCR and CBR. Best response is defined as the best observed response (CR>PR>SD>PD) throughout the study. See SAP table 1 for rules of response confirmation. Summaries will include the count and percentages and the 95% confidence intervals where appropriate of different best overall responses, ORR, DCR and CBR for each dose level. The percentages will be based on the total number of patients in the Full Analysis Set for a given Expansion Arm.

Waterfall and swimmer plots will also be created, similar to what is described for Phase 1, but additionally color coding of the Best Overall Response.

PK and ADA results matching Phase 1 secondary endpoints will be analyzed, but the presentation will be done by Expansion Cohort rather than by dose level. Analysis of Adverse Events is described in section 8.7.2.

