# 4.4. Study Duration

The total study duration will be approximately 12 months to complete the dose escalation phase (Phase 1) and from 24 to 48 months to enroll patients in and subsequently complete the expansion Phase (Phase 2a).

Patients may receive the investigational study treatment (AFM24 + atezolizumab) until disease progression, intolerable toxicity, Investigator discretion, or patient withdrawal of consent.

Patients may continue treatment after disease progression at their assigned dose if there is continuing clinical benefit per Investigator's judgment and in consultation with the Sponsor's Medical Monitor.

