#### 5.4.2. Premature Discontinuation

Every reasonable effort should be made to encourage retention of patients in the study, maximize compliance with study drug, and facilitate attendance at all scheduled study visits/assessments.

All patients have the right to refuse further participation in the study at any time and for any reason. A patient's participation must, therefore, be terminated immediately upon his/her request.

The Investigator will make every attempt to ascertain the reason(s) for discontinuation and to document this in detail in the source documentation and the appropriate sections of the eCRF. A patient must be withdrawn from the study for any of the following reasons:

- Withdrawal by patient or the patient's legal representative.
- Protocol violation/noncompliance (defined as refusal or inability to adhere to the study procedures).

- Confirmed progressive disease (PD), as assessed by the treating Investigator in accordance with RECIST v1.1 (On a case-by case basis, patients may continue treatment after disease progression at their assigned dose if there is continuing clinical benefit per Investigator's judgment and in consultation with the Sponsor's Medical Monitor).
- Symptomatic deterioration (clinical deterioration suggesting that no further benefit from treatment is likely). This category is applicable to patients with a global deterioration of health status requiring discontinuation of treatment. However, per RECIST v1.1, symptomatic deterioration is not a descriptor of an objective response (OR); it is a reason for stopping study therapy. Thus, every effort should be made to continue disease assessments per protocol until documented objective progression or initiation of alternate therapy.
- The development of a DLT (as defined in Section 4.2.3.1) during the dose escalation part (Phase 1) of the study.
- Pregnancy while receiving study drug.
- At the request of the Sponsor, regulatory agency, or IRB/IEC.
- Physician decision.
- Loss to follow-up.
- Death, otherwise not explainable by the above options.
- Patient may be withdrawn from study treatment due to unacceptable or intolerable AEs.

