# 8.6. Disease Response Assessment

Disease response will be assessed by the Investigator, using RECIST v1.1. For both the dose escalation phase (Phase 1) and expansion phase (Phase 2a), imaging results will be collected and preserved for future independent central review, if needed. Tumor assessment with CT and/or MRI will occur at Screening as well as during the last week of Cycles 2, 4, 6, 8, 10, 12 and every 3 cycles thereafter. Partial or CR needs to be confirmed with repeated assessment at least 4 weeks after the initial assessment.

If initial radiological PD is observed, while the clinical condition of the patient is stable, treatment continuation is allowed at the discretion of the Investigator and in consultation with the Sponsor's Medical Monitor. If treatment is continued after initial PD, a confirmatory scan should be acquired

within 4-6 weeks. However, the first successive scheduled timepoint after the confirmatory scan may be skipped if the window is considered not clinically relevant (up to the discretion of the Investigator). The next subsequent timepoint following the skipped timepoint must adhere to the original schedule.

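### SAP 8.6.2 takes best response over the whole study with no visible limit at progression, so read literally a response or stable disease first seen after PD raises ORR, DCR or CBR

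*SAP*

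**What the plan says.** SAP 8.6.2 gives the same rule for Phase 1 and Phase 2a: "Best response is defined as the best observed response (CR>PR>SD>PD) throughout the study". It also says: "Best overall response will be used to define the ORR, DCR and CBR". Both paragraphs refer to SAP Table 1 for response confirmation and say that investigators assess response by RECIST 1.1. Under SAP 8.6.1 the main visible statement concerns the population: "All the efficacy tables will be run for Full Analysis Set for Phase 1 and for Phase 2a". SAP section 10 replaces the protocol's DCR at fixed months with one overall DCR, so DCR now rests on best response as well.

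Protocol 8.3.2.1 defines ORR as the proportion with a best response of CR or PR by RECIST v1.1, and gives no time limit.

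The protocol provides for assessments after progression:
- Protocol 4.4: "Patients may continue treatment after disease progression at their assigned dose if there is continuing clinical benefit". Protocol 5.4.2 repeats this as a case-by-case exception to withdrawal: "patients may continue treatment after disease progression at their assigned dose if there is continuing clinical benefit".
- Protocol 8.6: "If treatment is continued after initial PD, a confirmatory scan should be acquired" within 4 to 6 weeks. After that, "the first successive scheduled timepoint after the confirmatory scan may be skipped if the window is considered not clinically relevant", and later scans return to the original schedule.
- Protocol 8.6 on confirmation: "Partial or CR needs to be confirmed with repeated assessment at least 4 weeks after the initial assessment". SD is not mentioned there.

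Two passages limit who is scanned after PD. Protocol 4.2.5.3 moves patients with confirmed progression to survival follow-up. Protocol 5.4.2 stops scans at progression or alternate therapy for patients who left treatment without confirmed progression.

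**The concern.** The SAP sentence sets both a window (the whole study) and a ranking in which PD loses to every other category. A patient who progresses, stays on treatment and later has a better reading is therefore classified by the better reading. ORR is the Phase 2a primary endpoint. It is investigator-assessed in an open-label study, and EXP-1 and EXP-2 use a Simon two-stage design. DCR is more exposed, because the visible text asks for no confirmation of SD.

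The rule also fits poorly with the time-to-event endpoints. PFS ends at progression (Protocol 8.3.2.3 and 9.3.2), and DOR ends at the first recurrence, PD or death (Protocol 8.3.2.4). If initial PD is the PFS event, a patient could have that event before the response that counts in ORR, and the end of that patient's DOR would be unclear. The protocol does not settle which PD is meant: it speaks of documented, initial and confirmed progression in different sections.

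**Working it through.** The documents give no figure to reproduce, so the check covers the rule, the scan calendar and the effect of one patient.

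**1. The rule applied to example sequences.** PR is taken as confirmed where two consecutive readings are shown.

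| Readings in order | Best over whole study | Best up to first PD | Rates that change |
|---|---|---|---|
| PD, SD, SD | SD | PD | DCR +1 |
| PD, PR, PR | PR | PD | ORR, DCR, CBR +1 |
| SD, PD, PR, PR | PR | SD | ORR +1; CBR +1 unless the SD already met 24 weeks |
| PR, PR, PD | PR | PR | none |
| PD | PD | PD | none |

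The best of a longer list is never worse than the best of its first part, so the shift is upward or zero. CBR follows ORR because Protocol 9.3.2 counts CR or PR of any duration.

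**2. Whether confirmation closes the gap.** Inputs from the protocol: 4-week cycles, scans in the last week of Cycles 2, 4 and 6, a confirmatory scan 4 to 6 weeks after PD, and response confirmation at least 4 weeks later. With C1D1 as Day 1, Cycle k Day d is Day 28(k−1)+d.
- Scan weeks: Cycle 2 Days 50–56, Cycle 4 Days 106–112, Cycle 6 Days 162–168.
- PD at Cycle 2 puts the confirmatory scan between 50+28 = Day 78 and 56+42 = Day 98.
- A PR on that scan can be confirmed at Cycle 4 only if seen by 112−28 = Day 84, and Day 84 works only if the Cycle 4 scan falls on Day 112.
- Day combinations: 7 PD days × 15 intervals (28–42 days) × 7 Cycle 4 days = 735. Those with at least 28 days between the two scans, for Cycle 4 Days 106 to 112 in turn, number 1+3+6+10+15+21+28 = 84, and 84/735 = 11%. This counts calendar combinations; it is not a probability.
- Otherwise Cycle 6 can confirm. From Day 98 it is 162−98 = 64 to 168−98 = 70 days later. A PR first seen at Cycle 4 has its Cycle 6 scan 162−112 = 50 to 168−106 = 62 days later. An unscheduled scan could also confirm.

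Confirmation narrows the route into ORR but does not close it. For DCR, the visible text sets no such condition.

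**3. Effect of one patient.** The shift is 1/n. Up to 130 patients in four cohorts (SAP 4.4) average at most 130/4 = 32.5 per cohort, and 1/32.5 = 3.1 points. Actual cohort sizes are not visible. For an assumed n of 20 to 45, the shift is 1/20 = 5.0 to 1/45 = 2.2 points.

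**The case against.** The strongest reply is that the rule is visible only in part. The sentence after the definition points to SAP Table 1, which is not shown, and most of SAP 8.6.1 is not shown either. Response is assessed by RECIST 1.1, which is not among the documents and may be meant to settle what can be recorded after PD. This stands as a limit. A reader might infer that the full plan has no cut-off at progression, or that SAP 8.6.2 alone defines ORR. The documents support neither, since the hidden text may hold a limit and Protocol 8.3.2.1 also defines ORR. But the reply does not rescue the sentence, whose stated window would contradict any limit placed elsewhere.

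Second, few patients are exposed. Confirmed PD normally leads to survival follow-up or withdrawal, and continuation is case by case. If only confirmed PD counts as progression, a response after an unconfirmed initial PD is not a response after PD at all. This stands, and it is why the finding claims no total effect.

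Third, swimmer plots (SAP 8.6.2) and patient listings (SAP 8.1) would show a late response. That helps a careful reader, but it does not change the reported rates.

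**Conclusion.** The concern holds for the visible text. As written, the window lets a confirmed PR or CR first seen after PD count in ORR, DCR and CBR, and lets SD after PD count in DCR. Against a window closed at PD, the shift can only be upward.

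The number of patients scanned after PD is unknown, so the total effect cannot be computed. The per-patient effect is 1/n: about 3.1 points at the average of 32.5, or 5.0 to 2.2 points for the assumed n of 20 to 45. A reader might infer that the primary result would be biased or a Simon decision reversed. That is not supported: the cut-offs and the primary-analysis text are not visible, and a decision changes only if the response count lies at the cut-off.

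This should be fixed before the SAP, still marked as a draft, is final. Confidence is medium because of the hidden text.

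**What to change.** In both places in SAP 8.6.2, end the best-response window at progression, for example: *up to and including RECIST v1.1 progression, using the same PD date as the PFS event*. State once whether that date is the initial or the confirmed PD, and use it for best response, PFS and DOR. Apply the window to ORR, DCR and CBR, and align SAP 8.6.1 and SAP Table 1 with it. List responses first seen after PD separately. A further cut-off at new anti-cancer therapy is optional, since the documents show no exposure there.

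The cost is one sentence in two places, one statement of the PD date and one derivation rule, with no new data. The downside is that ORR, DCR and CBR may be slightly lower, and patients who respond only after PD would appear in the separate listing and not in the rates.

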8.6.3 ANALYSIS OF EXPLORATORY EFFICACY ENDPOINTS AND ADDITIONAL ASSESSMENTS 
Phase 1 (Dose Escalation)

Review Status: Draft Version: 2.0 Version Date: 22-JUL-2024

Review Status: Draft Version: 2.0 Version Date: 22-1UI -2024

Frequency of patients developing neutralizing ADAs against AFM24 will be summarized.

Lymphocyte subset counts, including number of total and activated Natural Killer (NK) cells and macrophages, will be summarized by descriptive statistics at each visit for each dose level. Listing of Lymphocyte subset counts and NK cells will be created as a part of the laboratory listings.

#### Phase 2a (Expansion)

The exploratory endpoints and assessments for Phase 2a match the ones for the Phase 1, excluding PFS and DOR. Similar analyses will be performed, but the presentation will be done by Expansion Arm rather than by dose level.

#### 8.7 SAFETY ENDPOINTS AND ANALYSIS

Summaries for safety parameters will be done for the Safety Analysis Set for Phase 1 and Phase 2a. Tables will be presented by dose level for Phase 1 and by Expansion Arm for Phase 2a.

#### 8.7.1 EXPOSURE TO STUDY TREATMENT

Total exposure to the AFM24 and Atezolizumab in mg will be summarized by visit and overall. Total Duration of Exposure to AFM24 and Atezolizumab in weeks, Delays, Interruptions and Dose Adjustments and reasons for those, overall number of cycles, Dose Intensity and Relative Dose Intensity will be summarized as well. Listings of AFM24 and Atezolizumab exposure data (doses and all dose adjustments) will be created.

Dose Intensity for AFM24 or Atezolizumab will be defined as the total amount of AFM24 or Atezolizumab respectively received by the subject in mg divided by the Duration of Exposure. Relative Dose Intensity will be calculated as the total dose of AFM24 or Atezolizumab received divided by the planned dose of AFM24 or Atezolizumab respectively per cycle times the number of initiated cycles.

The Exposure data will be summarized both for DDS and the Safety Analysis Set in Phase 1, and for Safety Analysis Set in Phase 2a.

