#### **Dose cohorts**

Patients will be enrolled sequentially in cohorts of 3 to 6 patients into dose escalation phase (Phase 1). The dose escalation will follow 3+3 dose escalation design. In each cohort there will be at least 3 patients enrolled. The first 2 patients of each dose cohort will begin treatment in a staggered approach with at least 7 days between first dosing of these 2 patients. Subsequent patients may be enrolled concurrently. All patients who start treatment need to complete the 28-day DLT observation period or experience a DLT within the first cycle of treatment to be DLT evaluable. A minimum of 3 patients needs to be DLT evaluable per dose cohort. If no DLT is observed, the dose is escalated for the next cohort of 3 patients. If 1 DLT is observed, 3 additional patients will be treated at this dose level with dose escalation only if no additional DLTs occur. If less than 3 patients are evaluable for DLT assessment, replacement patient(s) will be enrolled. DLTs will be assessed in the first treatment cycle (i.e., the first 4 weeks of treatment for each patient, starting C1D1), referred to as the DLT observation period (28-days). Dose limiting toxicity will be defined by the criteria listed in Section 4.2.3.1. The number of patients included in each dose cohort may be increased from 3 up to 6 patients based on SRC decision to allow for further collection of safety, pharmacodynamic and PK data.

A 3+3 design will be used to determine the RP2D, with the schematic escalation rules given below. The number of patients with DLT at a given dose level will be evaluated as:

- 1. If 0 out of 3
  - Escalate to next higher dose level

#### 2. If 1 out of 3

- Enter 3 more patients at this dose level:
  - o If 0 of these additional patients experience a DLT, proceed to the next higher dose level
  - o If 1 or more of these additional patients experience a DLT, the dose escalation will be stopped. Up to 3 additional patients will be entered at the lower dose level if only 3 patients were treated previously at that dose level. Alternatively, up to 6 additional patients could be entered to receive intermediate dose levels, based on the emerging safety, PK, and pharmacodynamic data observed in the FIH AFM24-101 study If this occurs in Cohort 1, there will be a de-escalation to Cohort -1.

#### 3. > 2 out of 3

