# 6.4. Safety Lead-in Phase

Patients enrolling to the dose escalation phase (Phase 1) or the expansion phase (Phase 2a) will be evaluated for AFM24 hypersensitivity during safety lead-in phase as described in Section 4.2.2.

For the safety lead-in phase during the dose escalation phase (Phase 1), each patient will receive the AFM24 infusion on Day -7 at the dose according to the assigned cohort.

For the safety-lead in phase during the expansion phase (Phase 2a), each patient will receive the AFM24 infusion on Day -7 at the MTD/RP2D dose level, which is determined based on the dose escalation phase (Phase 1).

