## 6.7. Dose Interruptions, Delays, Modifications and Discontinuations

## **AFM24**

Treatment may be delayed for up to 3 weeks to allow sufficient time for recovery from treatment-related toxicities to baseline or Grade ≤1 (except for alopecia), except during the DLT observation period during the dose escalation phase (Phase 1). See Section 5.4.2 for criteria requiring permanent discontinuation of study treatment.

Dosing delays longer than > 3 weeks may be permitted in a case-by-case basis per the Investigator's judgement after consultation with the Medical Monitor. No dosing delays (including planned dosing delays such as elective surgery) will be allowed during the DLT observation period. Tumor assessments should continue as per protocol even if dosing is delayed.

If an AE occurs during the AFM24 infusion Safety Lead-in (D-7), and the dose is interrupted, the patient can restart upon recovery to baseline or Grade ≤1 within the same day. If the patient already received 80 mg of the prescribed dose of AFM24 on the day of dose interruption or cannot recover within the same day of the event, the rest of the dose should be omitted.

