#### Dose Modification:

During the dose escalation phase (Phase 1), if a patient is tolerating AFM24 in combination with atezolizumab well (i.e., no drug-related Grade ≥2 toxicity) without evidence of disease progression following 2 cycles, the patient may, beginning with Cycle 3 or a subsequent cycle, have the dose increased to a dose that has already been established as tolerable by the SRC, and with the agreement of the SRC.

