#### 4.2 SAFETY LEAD-IN PHASE

Seven days prior to Cycle 1 Day 1 (C1D1) (i.e., at Day -7 [minus 7]), patients will receive a single dose of AFM24 (dose assigned to a given cohort) and will be observed for any Adverse Event (AE) for 1 week (from Day -7 through Day -1 the safety lead-in phase). Patients who have any Grade ≥3 cytokine release syndrome (CRS) or infusion-related reaction (IRR) symptoms lasting >6 hours or any other possibly related Grade ≥3 non-hematological Treatment-Emergent Adverse Events (TEAE) or clinically significant hematological Grade ≥3 TEAEs during their safety lead-in phase will be permanently discontinued from the study. Patients not proceeding to combination therapy (AFM24 + atezolizumab) will be replaced.

#### 4.3 Phase 1

The aim of the dose escalation phase (Phase 1) is to determine the MTD/RP2D of AFM24 in

Review Status: Draft Version: 2.0 Version Date: 22-11.11 -2024

combination with atezolizumab.

The 160 mg i.v. qw dose was selected as the starting dose for the AFM24-102 study, based on the data obtained from the first in human study (AFM24-101). There were 2 additional dose escalations completed for AFM24, where the dose increase was based on data from the AFM24-101 study, in conjunction with the safety and PK data emerging from this study (see Protocol Section 2.4). Dose increases did not exceed 200% of the current dose. All dose escalation (and de-escalation) decisions were determined by the Safety Review Committee (SRC).

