#### 4.5 REPLACEMENT OF PATIENTS

In Phase 1 (dose escalation), a patient who did not fulfill the Dose Limiting Toxicity (DLT) requirements (refer to the protocol section **Error! Reference source not found.**) and who discontinued study participation prior to completing the DLT observation period due to any reason other than a DLT, would be replaced for DLT evaluation but will remain in the Safety Analysis Set (see Section 7.1 for definition).

For the dose escalation (Phase 1) and expansion phase (Phase 2a), all patients who begin AFM24 treatment (e.g. Day -7) but discontinue prior to receiving any amount of atezolizumab will be replaced but will remain in the overall Safety Analysis Set. A replacement patient will be enrolled and assigned the same cohort or dose level.

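### As written, AFM24 relative dose intensity counts the Day -7 dose as received but not as planned: full dosing reads above 100% and one missed dose reads as 100%

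*SAP*

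**What the plan says.** SAP 8.7.1 takes the total amount of AFM24 (or atezolizumab) received, "divided by the planned dose of AFM24 or Atezolizumab respectively per cycle times the number of initiated cycles". Nothing is excluded from the amount received, and the planned amount is built from cycles only. The section adds: "The Exposure data will be summarized both for DDS and the Safety Analysis Set in Phase 1".

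The lead-in infusion is given seven days before C1D1 at the dose assigned to the cohort (SAP 4.2). For Phase 2a, Protocol 6.4 says "each patient will receive the AFM24 infusion on Day -7 at the MTD/RP2D dose level". Protocol 4.2.3 (Dose cohorts) describes the first cycle as "the first 4 weeks of treatment for each patient, starting C1D1", so Day -7 lies outside Cycle 1. Protocol 4.1 also lists the lead-in separately from the treatment period.

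Three further provisions matter:

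- **Partial lead-in dose.** Protocol 6.7 has the remainder of an interrupted lead-in infusion omitted in some cases: "If the patient already received 80 mg of the prescribed dose of AFM24 on the day of dose interruption" is one trigger.
- **Lead-in-only patients.** Under SAP 4.5, patients who begin AFM24 but "discontinue prior to receiving any amount of atezolizumab will be replaced but will remain in the overall Safety Analysis Set".
- **Dose increase.** From Cycle 3 onward, a Phase 1 patient who tolerates treatment may "have the dose increased to a dose that has already been established as tolerable by the SRC" (Protocol 6.7).

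**The concern.** RDI is normally read as the share of the planned dose that was given. Here one full AFM24 dose is in the numerator with no counterpart in the denominator. Three problems follow:

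- A patient who missed nothing reads above 100%, and one missed dose can be cancelled out by the lead-in dose.
- The excess depends on time on treatment and on schedule. It is largest in patients who stop early and doubles under the optional q2w schedule, so values are not comparable across durations or schedules. Atezolizumab has no lead-in dose, so the two drugs' RDIs would have different meanings in one exposure summary.
- Lead-in-only patients belong to the Safety Analysis Set (SAP 4.5 and 7.1) but have zero initiated cycles. Their RDI is a division by zero, and they would drop out of the n that SAP 8.1 requires with each summary.

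**Working it through.** The documents state no RDI figure, so there is none to reproduce. The check applies the SAP formula directly.

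**Inputs.** D = AFM24 dose, 480 mg at the RP2D (SAP 4.6.2). m = planned AFM24 doses per 4-week cycle: 4 weekly, 2 if q2w (SAP 4.6). k = initiated cycles. g = in-cycle doses given. L = lead-in amount delivered, equal to D if complete.

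**Formulas.**

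- As written: RDI = (L + gD) / (mkD)
- Lead-in in both terms: (L + gD) / (D + mkD)
- Lead-in in neither term: gD / (mkD)

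**Weekly, constant dose, full lead-in, every initiated cycle completed.** With nothing omitted g = 4k; with one in-cycle dose omitted g = 4k - 1.

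| k | Nothing omitted, as written (4k+1)/(4k) | One omitted, as written 4k/(4k) | One omitted, in both 4k/(4k+1) | One omitted, in neither (4k-1)/(4k) |
|---|---|---|---|---|
| 1 | 5/4 = 125% | 100% | 4/5 = 80% | 3/4 = 75% |
| 2 | 9/8 = 112.5% | 100% | 8/9 = 88.9% | 7/8 = 87.5% |
| 3 | 13/12 = 108.3% | 100% | 12/13 = 92.3% | 11/12 = 91.7% |
| 6 | 25/24 = 104.2% | 100% | 24/25 = 96.0% | 23/24 = 95.8% |

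The first on-treatment scan falls in the last week of Cycle 2 (Protocol 8.6), so a weekly patient who leaves at that scan shows at most 112.5%.

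**q2w, if used, nothing omitted:** (2k+1)/(2k) = 150%, 125% and 116.7% at 1, 2 and 3 cycles.

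**Atezolizumab, nothing omitted:** 2k × 840 / (2k × 840) = 100%.

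**Shortened lead-in (80 of 480 mg), one weekly cycle.** Nothing omitted: (80 + 1920)/1920 = 104.2%. One dose omitted: (80 + 1440)/1920 = 79.2%. Exact masking therefore needs a full lead-in dose.

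**DDS example.** A weekly patient with one initiated cycle and 3 of 4 infusions is exactly at the 75% Cycle 1 limit in SAP 7.3. The RDI reads (480 + 3 × 480)/1920 = 100%.

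**Dose increase.** This illustration uses the two dose levels in SAP 4.6.1: 160 mg, then 480 mg from Cycle 3, with three full weekly cycles. Received: 160 + 8 × 160 + 4 × 480 = 3360 mg.

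| Rule | Original dose counted as planned | Dose in force counted as planned |
|---|---|---|
| As written | 3360/1920 = 175% | 3360/3200 = 105% |
| Lead-in in both | 3360/2080 = 161.5% | 3360/3360 = 100% |
| Lead-in in neither | 3200/1920 = 166.7% | 3200/3200 = 100% |

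**The case against.** **The SAP never names Day -7 in the RDI definition.** If the programmers leave it out, or count it as planned, the excess disappears. The text under Handling of Missing Data is not in the public copy, and the table shells are in a separate document. This stands as a limit on what can be said about the actual tables. It does not rescue the wording: an unqualified total received includes Day -7, and SAP 4.5 itself gives Day -7 as an example of beginning AFM24 treatment.

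**The same formula also pulls the other way.** An initiated cycle counts in full, so stopping mid-cycle lowers RDI. A weekly patient who receives every dose and stops after C1D8 reads 3/4 = 75% as written, 3/5 = 60% with the lead-in in both terms and 2/4 = 50% with it in neither. After C3D1 the values are 10/12 = 83.3%, 10/13 = 76.9% and 9/12 = 75%. This stands: the percentages above 100% are upper bounds for their cycle counts at a constant dose, and the net direction across patients is unknown. But it is a separate feature of counting initiated cycles. It does not justify the mismatched lead-in dose.

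**Little depends on RDI.** This also stands. SAP 8.7.1 separately reports mg by visit, delays, interruptions, adjustments and listings, and DDS membership rests on Cycle 1 dose rather than RDI. The dose-increase case is optional and needs SRC agreement, and nothing in the documents shows that it occurred.

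**Conclusion.** The concern holds, as a minor point. Followed literally, SAP 8.7.1 overstates AFM24 RDI by the lead-in amount delivered divided by the planned in-cycle amount. With a full lead-in dose that is 1/(4k) weekly: 25, 12.5, 8.3 and 4.2 percentage points at 1, 2, 3 and 6 cycles. It is twice that on q2w. One omitted in-cycle dose is masked exactly when the dose is constant, the lead-in was complete and there is no other shortfall. Atezolizumab RDI is not inflated. Lead-in-only patients have no calculable value; their number is not known from the documents.

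The conclusion rests on reading the amount received as including Day -7. The definition does not say so expressly, and no visible text says otherwise. Efficacy conclusions, DLT assessment and dose selection are unaffected.

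**What to change.** Adopt one rule for AFM24 and write it into SAP 8.7.1:

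- **Option (a), lead-in in both terms.** Divide the total received by the assigned lead-in dose plus the planned dose per cycle, on the assigned schedule, times initiated cycles. Lead-in-only patients then have a defined value. The drawback is that a patient who completes the lead-in infusion and is then discontinued reads 480/480 = 100%. A shortened lead-in shows as a shortfall: 80 of 480 mg gives 2000/2400 = 83.3% after one full weekly cycle, or 80/480 = 16.7% if nothing follows.
- **Option (b), lead-in in neither term.** Drop Day -7 from the numerator, report it in its own row, and show RDI as not calculated for patients with no cycle. A shortened lead-in then appears only in that row.

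Under either option, show atezolizumab RDI as not calculated when no cycle was started. State which dose counts as planned for Phase 1 patients whose dose was increased; otherwise values above 100% can remain. A sentence noting that initiated cycles count in full would help readers interpret low values after a mid-cycle stop, which neither option changes.

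The cost is a few lines of SAP text and programming, with no new data; the SAP is still marked as a draft. Reported AFM24 RDI falls, by the percentage points in the verdict for fully dosed weekly patients.
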